Table 1.	Corticosteroid Regimens and Doses Recommended or Required	17
Table 2.	Renal Monitoring Parameters and Actions To Be Taken	25
Table 3.	Schedule of Events (Double-Blind Treatment Period)	31
Table 4.	Schedule of Events (Open-Label Treatment Period)	32
Table 5.	Relationship of Study Drug to Adverse Event	43
Table 6.	Grading of Adverse Event Severity	44
Table 7.	Investigator Site Reporting Requirements for Adverse Events	45

LIST OF APPENDICES

APPENDIX 1	MANAGEMENT OF CORTICOSTEROIDS	76
------------	-------------------------------------	----

LIST OF ABBREVIATIONS AND DEFINITION OF TERMS

Term	Definition
6MWD	6-minute walk distance
6MWT	6-minute walk test
ACE	angiotensin-converting enzyme
AE	adverse event
ALT	alanine aminotransferase
ANCOVA	analysis of covariance
ARB	angiotensin receptor blockers
AST	aspartate aminotransferase
ATC	Anatomical Therapeutic Chemical
BB	Beta-blocker
Bi-PAP	bi-level positive airway pressure
BUN	blood urea nitrogen
CD40	cluster of differentiation 40
CD-ROM	compact disk read-only memory
cGMP	current good manufacturing practice
CI	confidence interval
CK	creatine kinase
CRF	case report form
CRO	contract research organization
CTCAE	Common Terminology Criteria for Adverse Events
CYP	cytochrome P450 enzyme
DMD	Duchenne muscular dystrophy
DMDSAT	DMD Functional Ability Self-Assessment Tool
DNA	deoxyribonucleic acid
EC	ethics committee
ECG	Electrocardiogram
eCRF	electronic case report form
EDC	electronic data capture
EMA	European Medicines Agency
EQ-5D	EuroQoL 5-Dimension
FDA	Food and Drug Administration
FVC	forced vital capacity
GCP	good clinical practice
GGT	gamma-glutamyl transferase
HDL	high-density lipoprotein
HRQL	health-related quality of life
ICH	International Council for Harmonisation
ID	Identification
IRB	institutional review board
IRT	interactive response technology
ITT	intention-to-treat
IV	intravenous
LDH	lactate dehydrogenase
LDL	low-density lipoprotein
LTBP4	latent TGF-beta binding protein 4
MAR	missing at random
MedDRA	Medical Dictionary for Regulatory Activities
mITT	modified intention-to-treat
MMRM	mixed model for repeated measures
MRI	magnetic resonance imaging
MRS	magnetic resonance spectroscopy

Term	Definition
mRNA	messenger ribonucleic acid
nmCF	nonsense mutation cystic fibrosis
nmDMD	nonsense mutation Duchenne muscular dystrophy
NSAA	North Star Ambulatory Assessment
OAT1	organic anion transporter 1
OAT3	organic anion transporter 3
OATP1B3	organic anion transporting polypeptide 1B3
PROM	Patient-Reported Outcome Measure
PUL	Performance of Upper Limb
RSI	reference safety information
SAE	serious adverse event
SAP	statistical analysis plan
SD	standard deviation
SOP	standard operating procedure
SPP1	secreted phosphoprotein 1
TEAE	treatment-emergent adverse event
TFTs	timed function tests
ULN	upper limit of normal
WHODRUG	World Health Organization Drug Dictionary

1 INTRODUCTION

1.1 Disease Background

Duchenne muscular dystrophy (DMD) is a rare genetic disorder caused by mutations in the gene encoding dystrophin, a protein expressed in skeletal, respiratory, and cardiac muscle [Bushby 2010a, Bushby 2010b]. The role of the dystrophin protein is to act as a shock absorber, bearing the mechanical stresses that occur during muscle contraction, stabilizing muscle cell membranes, and protecting muscles from injury [Petrof 1993]. In the absence of dystrophin, the stress placed on the membranes during contractions causes them to tear. Degeneration of muscle fibers attracts inflammatory cells, ultimately resulting in the replacement of healthy muscle with fatty and fibrosis tissue.

Muscle weakness in the lower-extremity muscles generally becomes apparent in the first few years of life, with delays in motor milestones such as attainment of independent walking [Bushby 2010a]. Deterioration of ambulation occurs in the first decade of life and wheelchair dependency in the teen years [Bushby 2010a]. Muscle weakness eventually develops in the upper-extremity muscles as well as respiratory and cardiac muscles, and respiratory or cardiac failure typically results in death by the third decade [Passamano 2012].

There is no cure for DMD. Treatments aimed at maintaining ambulation for as long as possible and managing the musculoskeletal complications of DMD include corticosteroids, physical therapy interventions involving gentle exercise and activity, and surgery to prevent or minimize lower-limb contractures and deformities [Bushby 2010a, Bushby 2010b]. The use of corticosteroids, previously controversial due to side effects, has increased since the publication of clinical management guidelines in 2010 strongly urging consideration of glucocorticoid therapy in all patients with DMD [Bushby 2010a, Bushby 2010b]. As the disease progresses, respiratory (eg, mechanical ventilation) and cardiac (eg, angiotensin-converting-enzyme inhibitors) interventions are employed [Bushby 2010a, Bushby 2010b].

Approximately 10 to 15% of boys with DMD have the disease due to a nonsense mutation [Aarstma-Rus 2006, Bladen 2015]. A nonsense mutation in deoxyribonucleic acid (DNA) results in a premature stop codon in the protein-coding region of the corresponding messenger ribonucleic acid (mRNA). When a premature stop codon is present, ribosomal translation of mRNA is interrupted before a full-length, functional protein is generated.

1.2 Ataluren

Ataluren promotes ribosomal readthrough of premature stop codons, enabling the formation of full-length, functional dystrophin protein [Welch 2007]. Because of the role of the dystrophin protein, dystrophin restoration therapy would be expected to stabilize or slow disease progression in patients with DMD [Merlini 2015].

The efficacy and safety of ataluren as a treatment for nonsense mutation Duchenne muscular dystrophy (nmDMD) previously were assessed in 2 randomized, double-blind, placebo-controlled, 48-week trials (NCT00592553 and NCT01826487, respectively). Data from these studies supported conditional marketing authorization of ataluren for the treatment of nmDMD in ambulatory patients aged ≥ 5 years in Europe, with a specific obligation to confirm the efficacy and safety of ataluren in this population by conducting a randomized, double-blind, placebo-controlled, 72-week study followed by a 72-week open-

label extension. This protocol describes the randomized, double-blind, placebo-controlled, 72-week study and its 72-week open-label extension.

A detailed description of the chemistry, pharmacology, efficacy, and safety of ataluren is provided in the current Investigator's Brochure.

2 STUDY OBJECTIVE AND ENDPOINTS

2.1 Objectives

2.1.1 Primary Objective

The primary objective of this study is to determine the effect of ataluren on ambulation and endurance as assessed by the 6-minute walk test (6MWT).

2.1.2 Secondary Objectives

The secondary objectives of this study are to:

- Determine the effects of ataluren on ambulation and burst activity as assessed by timed function tests
- Determine the effects of ataluren on lower-limb muscle function as assessed by the North Star Ambulatory Assessment (NSAA)
- Assess the safety profile of ataluren
- Evaluate the correlation between plasma concentration of ataluren and functional outcomes
- Evaluate the plasma pharmacokinetic (PK) profile of ataluren

2.1.3 Exploratory Objectives

The exploratory objectives of this study are to:

- Determine the effects of ataluren on upper-limb muscle function strength as assessed by the Performance of Upper Limb (PUL) and by the DMD Upper Limb PROM (in subjects ≥ 7 years old at baseline)
- Determine the effects of ataluren on muscle strength as assessed by myometry (in subjects < 7 years old at baseline)
- Determine the effects of ataluren on skeletal muscle integrity as assessed by magnetic resonance imaging (MRI) (at pre-qualified sites only)
- Determine the effects of ataluren on subject- and parent/caregiver-reported health-related quality of life (HRQL) as assessed by at-home questionnaire
- Determine the effects of ataluren on pulmonary function as assessed by forced vital capacity (FVC)

2.2 Endpoints

2.2.1 Double-Blind Treatment Period

The efficacy endpoints below focus on the comparison of ataluren versus placebo in the double-blind treatment period (baseline to Week 72).

2.2.1.1 Primary Endpoint

The primary endpoint of this study is slope of change in 6-minute walk distance (6MWD) over 72 weeks.

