2.2.1.2 Secondary Endpoints

- Change from baseline to Week 72 in 6MWD
- Composite of average change in times to run/walk 10 meters, climb 4 stairs, and descend 4 stairs at Week 72
- Change from baseline to Week 72 in time to run/walk 10 meters
- Change from baseline to Week 72 in time to climb 4 stairs
- Change from baseline to Week 72 in time to descend 4 stairs
- Change from baseline to Week 72 in NSAA total score
- Time to loss of ambulation over 72 weeks
- Time to loss of stair-climbing over 72 weeks
- Time to loss of stair-descending over 72 weeks
- Risk of loss of NSAA items over 72 weeks
- Ataluren safety profile characterized by type, frequency, severity, and relationship to study drug of any adverse events (AEs), or of abnormalities of laboratory tests, vital signs, physical examinations, or electrocardiograms (ECGs)

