2.3. Study Endpoints for Double-Blind Treatment Period

2.3.1. Primary Endpoint

The primary endpoint is slope of change in 6MWD over 72 weeks.

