6.1.2. Primary Analysis

The rate of change in 6MWD over 72 weeks (slope) in the mITT population will be considered as the primary efficacy endpoint.

A MMRM model will be employed using a random intercept and a random slope of change per week using observed data assuming the missing assessments are MAR. The slope will be compared between ataluren and placebo, and the estimated treatment difference with corresponding 95% confidence interval (CI) will be provided. The estimated difference in the change at Week 72 will also be provided to facilitate interpretation. The MMRM model will include baseline concomitant corticosteroid type (deflazacort, prednisone/prednisolone), baseline 6MWD category (<300 meters, 300 to <350 meters, 350 to <400 meters, ≥400 meters), baseline 6MWD, treatment, week (actual week at the visit as a continuous variable), the interaction of week and baseline 6MWD, and the interaction of week and treatment. The unstructured covariance matrix (UN) will be used in the MMRM model. Other types of covariance matrix (heterogenous Toeplitz, Toeplitz, and compound symmetric) will be explored in the case of non-convergence of UN. For this analysis, any subjects who lose ambulation during the study will be assigned a 6MWT result of 0 meters for the first visit in which the subjects lose ambulation and set for missing for all visits afterwards while they participate in the study.

The primary endpoint will be tested at the significance level of 0.05 (two-sided). If $p < 0.05$, then the primary endpoint will be considered statistically significant, and the study will be declared positive.

The example SAS code is listed below:

```
PROC MIXED data=<dataset> method=reml;  
  CLASS Cortico Subjid Trt C6WMD;  
  MODEL N6WMD = Cortico C6WMD Trt B6WMD Week Week*B6WMD  
    Week*TRT/S CL;  
  RANDOM Int Week/type=un subject=Subjid;  
  LSMEANS TRT / pdiff at Week=72 CL;  
RUN;
```

where

N6WMD = 6WMD at each visit (Baseline to Week 72)

B6WMD = Baseline 6WMD
C6WMD = Baseline 6WMD category
Cortico = Baseline concomitant corticosteroid type
Week = Actual study week at each visit
Trt = Treatment group
Subjid = Subject
Int = Intercept

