3. CHANGE FROM PLANNED EFFICACY EVALUATION

3.1. Primary Efficacy Variable (6MWD)

There is no change in the primary efficacy endpoint, the mean rate of change from baseline in 6MWD over the 72-weeks of treatment. As explained in Section 2 the MMRM model was modified from a linear regression MMRM to a MMRM model with visit time as a categorical variable to account for the nonlinearity of study data.

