3.1.1. Primary Analysis

The average rate of change from baseline in 6MWD over 72-weeks of treatment in the ITT population is considered the primary efficacy endpoint of interest for this study. The ITT population was specified in the original SAP as a supportive population for the primary endpoint analysis given its importance in providing information on the broad study population (N=359) encompassing the full range of age and ambulatory function. The MMRM category model with a random intercept, baseline 6MWD as a covariate, and factors of baseline concomitant corticosteroid type (deflazacort, prednisone/prednisolone), baseline 6WMD category (<300 meters, 300 to <350 meters, 350 to <400 meters, ≥400 meters), baseline time to stand from supine (<5 seconds, ≥5 seconds), treatment, visit (analysis visit as a categorical variable), interaction of visit and treatment, interaction of visit and baseline 6MWD, and unstructured covariance matrix (UN), is considered the primary analysis model of interest. In case of non-convergence, other types of covariance matrix are to be used in the order of heterogenous Toeplitz, Toeplitz, and compound symmetric. For this analysis, any subject who lose ambulation during the study was assigned a 6MWD of 0 meters for the first visit in which the subjects lose ambulation and set to 0 meters for all subsequent visits while they participate in the study. The average rate of change in 6MWD over 72-weeks of treatment is calculated from the estimated change from baseline in 6MWD at Week 72 from the MMRM categorical model.

A sample code is listed as below:

```
PROC MIXED data=<dataset> method=reml;  
  CLASS Cortico C6MWD TTSTBLC Subjid Trt AVISIT;  
  MODEL CHG6WMD = Cortico C6WMD TTSTBLC Trt B6WMD AVISIT  
                  AVISIT*B6WMD AVISIT*TRT/CL;  
  RANDOM Int / subject=Subjid;  
  REPEATED AVISIT / type=un subject=Subjid;  
  LSMEANS TRT*AVISIT / pdiff CL;  
RUN;
```

where

CHG6WMD = Change from baseline in 6WMD at each visit (Baseline to Week 72)
B6WMD = Baseline 6WMD
C6WMD = Baseline 6WMD category
Cortico = Baseline concomitant corticosteroid type
TTSTBLC = Time to stand from supine category
AVISIT = Analysis visits as categorical variable
Trt = Treatment group
Subjid = Subject

Int = Intercept

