3.2.2. Other Secondary Efficacy Variables

The other secondary efficacy endpoints remain the same as the prespecified endpoints, with the primary population of interest being ITT and the primary analysis model of interest being the MMRM categorical model, where applicable.

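### The primary endpoint declared unchanged is no longer the prespecified 72-week 6MWD slope but the Week 72 change, a separate secondary endpoint, divided by 72

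*Protocol*

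**What the plan says.** Two 6MWD endpoints were set out in advance. Protocol 2.2.1.1 makes the slope primary: "The primary endpoint of this study is slope of change in 6-minute walk distance (6MWD) over 72 weeks". Protocol 2.2.1.2 lists "Change from baseline to Week 72 in 6MWD" among the secondary endpoints. The double-blind SAP (version 1.0) repeats the split. Its 2.3.1 reads "The primary endpoint is slope of change in 6MWD over 72 weeks", and its 2.3.2 puts the Week 72 change under other secondary endpoints. Its 6.1.2 fixes the method for the slope: "A MMRM model will be employed using a random intercept and a random slope of change per week using observed data", with actual week as a continuous variable and the slopes compared between arms in the mITT population. The Week 72 difference is given there only as an aid to interpretation.

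The document that sets out changes from the planned analysis for EMA/MHRA (below, the changes document) replaces this model with one that treats visit as a category, in the ITT population. On the endpoint, its 3.1 says: "There is no change in the primary efficacy endpoint, the mean rate of change from baseline in 6MWD over the 72-weeks of treatment". On the derivation, its 3.1.1 says the average rate "is calculated from the estimated change from baseline in 6MWD at Week 72 from the MMRM categorical model". On the rest, its 3.2.2 says: "The other secondary efficacy endpoints remain the same as the prespecified endpoints".

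Open-label SAP version 2.0 adopts the same categorical model. In its section 8 it lists the removal of the 144-week 6MWD slope as a major change, and in section 9 it attributes this to alignment with the changes document.

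**The concern.** A slope fitted to all visits and a Week 72 change divided by 72 are guaranteed to be the same quantity if the treatment difference grows linearly. Section 2.1 of the changes document drops the linear model because, after database lock, linearity was judged not to hold. It therefore cannot rely on linearity to say that the endpoint is the same. If the statement in 3.1 stands, a confirmatory study will report as its primary result something that protocol and SAP both classed as secondary, and a reader will be told that nothing moved. This point is about which quantity is estimated. It does not rest on the move from mITT to ITT, or on whether the linear model fitted badly.

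**Working it through.** **1. The planning figure is on the slope scale.** Inputs from the double-blind SAP, 2.4: difference 1.0 m/week, SD 2.058 m/week, two-sided alpha 0.05, power 85%, 1:1 allocation.

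n per arm = 2 × (1.960 + 1.036)² × 2.058² / 1.0² = 76.1, so 77 per arm and 154 in total, as stated. Adding 5% gives 154 × 1.05 = 161.7, so 162, as stated. (154/0.95 gives 163.)

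**2. The rate in Table 1 of the changes document (mITT) is the Week 72 difference divided by 72.**

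| Row | Week 72 difference (SE), m | ÷ 72 | Printed rate (SE), m/week |
|---|---|---|---|
| Descriptive | 8.99 | 0.125 | 0.12 |
| Linear MMRM | 9.95 (14.9) | 0.138 (0.207) | 0.14 (0.207) |
| ANCOVA after MI | 9.10 (13.1) | 0.126 (0.182) | 0.13 (0.182) |
| Categorical MMRM | 8.26 (9.1) | 0.115 (0.126) | 0.11 (0.126) |

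All rows agree within rounding. In the linear row this follows from the model, because a fitted slope times 72 is the fitted Week 72 change. In the categorical row there is no slope parameter. The sample code in 3.1.1 has no continuous week term and outputs treatment-by-visit means, so the rate can only be the Week 72 estimate rescaled.

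**3. Rescaling does not change the test.** Categorical model: z = 8.26/9.1 = 0.91, two-sided p about 0.36, and the same after dividing both figures by 72. The prespecified slope analysis is a different test: z = 9.95/14.9 = 0.67, p about 0.50. (Normal approximation throughout.)

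**4. The two quantities weight the visits differently.** For illustration, take equally spaced visits at Weeks 0, 12, …, 72. The mean time is 36 and the sum of squared deviations is 2 × (36² + 24² + 12²) = 4032. A least-squares slope weights each visit by (t − 36)/4032:

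| Week | 0 | 12 | 24 | 36 | 48 | 60 | 72 |
|---|---|---|---|---|---|---|---|
| Slope | −0.0089 | −0.0060 | −0.0030 | 0 | 0.0030 | 0.0060 | 0.0089 |
| Week 72 change ÷ 72 | −0.0139 | 0 | 0 | 0 | 0 | 0 | 0.0139 |

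The two agree under linearity and for some other shapes, such as a quadratic, but not in general. The mixed model in SAP 6.1.2 uses actual weeks and random slopes, so its weights are not exactly these, but it too draws on all visits.

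**5. The sponsor's two documents side by side.** On adopting the categorical model, open-label SAP 2.0 records the 144-week slope as removed. Its 6.2.1 then uses an average rate taken from the Week 144 estimate. The changes document makes the same move at Week 72 and records no change of endpoint. Both descriptions cannot be right.

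**The case against.** The best defence is that an average rate over the interval is a fair reading of a slope over 72 weeks. SAP 6.1.2 itself describes the endpoint as a rate of change. SAP 2.4 states the hypothesis as a slope from baseline to Week 72 and then defines only those two distances, so the sizing section alone does not settle that an all-visit fitted slope was meant. That much stands. But 6.1.2 specifies the slope as a model parameter over continuous week. If the Week 72 change divided by 72 had been the same endpoint, listing the Week 72 change separately would have been redundant.

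Nor is the derivation hidden. Section 3.1.1 says where the rate comes from, and Table 1 prints the prespecified linear result beside the new one. That is true. The fault is the statement of no change, not concealment.

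A reader might also infer more than the documents support:

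- *That one test will be reported twice, or that the type I error is inflated.* Section 3.2.2 keeps the secondary list with the same population and, where it applies, the same model, which implies a risk of double counting. No subsection plans a second report. The Week 72 change in 6MWD is outside the fixed test sequence (SAP 4.6), so alpha is not affected.
- *That the division in Table 1 alone proves the switch.* It holds in every row, including the linear one. The proof is the derivation in 3.1.1 together with the absence of a slope in that model.
- *That the gap between 9.95 (14.9) and 8.26 (9.1) measures the change of endpoint.* The analysis in 3.1.1 also uses change from baseline as the response, drops the random slope, uses analysis visits instead of actual weeks, and keeps visits after loss of ambulation at 0 m where SAP 6.1.2 set them to missing. These effects cannot be separated.

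**Conclusion.** The statement in 3.1 of the changes document is wrong. The quantity reported as primary is the protocol's secondary endpoint in other units, with the same test, and under the document's own finding of non-linearity it is in general not the prespecified slope. This rests on the text of the documents and on the categorical row of Table 1.

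Its numerical effect cannot be stated. The by-visit differences are not available, and any figure for the gap between slope and average rate would need an assumed time course. Table 1 is for mITT; no ITT estimate is given, but dividing by 72 leaves the test unchanged in any population. In the reported mITT data neither analysis is significant (p about 0.50 and 0.36), and the prespecified estimate is the larger and less precise (0.14, SE 0.207, against 0.11, SE 0.126, m/week). What changes is which result may be called primary.

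**What to change.** 1. In 3.1 of the changes document, delete the statement that the primary endpoint is unchanged, and state that the primary estimand changed after database lock.
2. Keep the prespecified mITT slope analysis (SAP 6.1.2; 0.14 m/week, SE 0.207, in Table 1) as the primary result.
3. Label the categorical-model Week 72 estimate, in metres or divided by 72, as a post hoc analysis of the secondary endpoint "Change from baseline to Week 72 in 6MWD", and report it once.
4. If a slope that does not assume linearity is wanted, add a linear contrast of the visit-specific differences from the categorical model as a labelled post hoc sensitivity analysis. It uses nominal visits and was not prespecified, so it is a third quantity and should not become the primary.

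The cost is wording and, for item 4, one extra estimate from a model already fitted. No new data are needed. The downside is that the headline result carries the larger standard error of the prespecified model.

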2.2.1.2 Secondary Endpoints

- Change from baseline to Week 72 in 6MWD
- Composite of average change in times to run/walk 10 meters, climb 4 stairs, and descend 4 stairs at Week 72
- Change from baseline to Week 72 in time to run/walk 10 meters
- Change from baseline to Week 72 in time to climb 4 stairs
- Change from baseline to Week 72 in time to descend 4 stairs
- Change from baseline to Week 72 in NSAA total score
- Time to loss of ambulation over 72 weeks
- Time to loss of stair-climbing over 72 weeks
- Time to loss of stair-descending over 72 weeks
- Risk of loss of NSAA items over 72 weeks
- Ataluren safety profile characterized by type, frequency, severity, and relationship to study drug of any adverse events (AEs), or of abnormalities of laboratory tests, vital signs, physical examinations, or electrocardiograms (ECGs)

